14. HUMAN SUBJECTS

All study staff will complete the web-based Collaborative Institutional Training Initiative (CITI) for Basic Human Subjects Research, Conflict of Interest Training and training in the Health Insurance Portability and Accountability Act (HIPAA). All study participants have a waiver of documentation of written consent using procedures reviewed and approved by Johns Hopkins Institutional Review Boards. The consent scripts cover all procedures done as part of data collection and the intervention.

Sources of materials

Data collectors will conduct assessments in-person and/or remotely. Eligibility will be determined through baseline data collection procedures for each study population. To determine eligibility for the study for consumer participants, we will also obtain permission from potential subjects to talk with mental health program staff and clinicians and contact their primary care physician and psychiatrist concerning any medical or psychiatric reasons for study exclusion. We will communicate with these physicians to ensure there are no contraindications to participating in the intervention. We will document assessments in each subject's study chart.

Safety Monitoring for Consumer Participants

Consumer participant safety will be closely monitored. Protection of these research participants begins with the eligibility criteria, which are designed to exclude individuals with a serious medical condition or psychiatric instability that would make it unsafe for them to take part in a weight-loss program. During the study, regular mental health and primary care will be provided by the participant's usual mental health and primary care providers, not by the study. Participants will be made aware of this delineation of responsibility.

We will carefully monitor the safety of enrolled participants. If a participant develops a medical or psychiatric issue, the safety of continuing or resuming participation in the weight-loss program will be ascertained by the study clinician in collaboration with the participant's regular providers. Surveillance for serious adverse events and other relevant clinical events will occur at the six-month mark.

A study clinician, [name] (independent study monitor), with appropriate expertise will be responsible for reviewing medical eligibility criteria and clinical measures, and will be the primary contact for staff, participants and physicians for medical issues. This clinician will review and report any serious adverse events and will have appropriate coverage during absences to provide 24/7 medical safety coverage for the study.

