3. BACKGROUND & SIGNIFICANCE

Public health burden of CVD, obesity, and other CVD risk factors in persons with SMI

CVD is the leading cause of preventable death among persons with SMI⁴⁻¹⁰, and this population has high prevalence of CVD and CVD risk factors²²⁻²⁶. Notably, obesity is extremely common¹⁻³. For example, 60% of women with SMI have obesity^{2,27,28} as compared to 41% of women in the general population²⁹.

Factors that contribute to obesity in individuals with SMI

Several factors contribute to the high obesity prevalence. First, the vast majority of individuals with SMI take at least one long-term psychotropic medication, and these drugs promote weight gain due to increased appetite along with metabolic abnormalities such as elevated glucose and lipids³⁰⁻³⁶. A shared decision-making process that provides patients with the expected weight and metabolic effects of these medications has been the recommended strategy to clinicians to make an informed decision about choice³⁷. Unfortunately, initial selection of or changes to a weight-neutral alternative medication may not be an option for many individuals with SMI; therefore, medications are unlikely to be a modifiable risk factor.

Second, diet and physical activity are typically poor in this population. Studies of individuals with SMI demonstrate high calorie and fat intake, as well as low intake of fruit and vegetables³⁸⁻⁴³. Physical activity levels are low in this population⁴⁴⁻⁴⁸. For example, persons with SMI report 50% higher leisure time inactivity than the general population⁴⁵, and an accelerometry study showed only 4% of individuals with SMI met recommended moderate to vigorous physical activity in bouts of ≥ 10 minutes⁴⁸. These lifestyle habits also contribute to obesity and CVD risk among individuals with SMI, and unlike psychotropic medications, represent a modifiable CVD risk factor.

Challenge of behavioral weight-loss interventions among persons with SMI

In general populations, behavioral weight-loss interventions have been demonstrated to improve CVD risk by reducing blood pressure and glucose, as well as improving lipid profiles¹¹. Behavioral interventions promoting healthy diet, exercise, and weight loss are critically needed, but must be adapted to challenges particularly to the SMI population. In particular, memory impairment, limited executive function, and residual psychiatric symptoms^{12,13}.

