7.3 Measurements

Measurements will be conducted using standardized operating procedures and quality control methods. Specific study forms either in RedCap or paper will be used to collect data.

Table 5. Data Collection Schedule for Consumers

		Follow-up
--	--	-----------

	Screening/ Baseline	During	6M Post
General Assessments			
Evaluation to Give Consent	x		
Demographics	x		
Exercise pre-participation screening (modified 2018 PAR-Q)	x		
Medical history	x		
Medications	x		x
Readiness rulers	x		
Physical Measurements			
BMI	x		x
Blood pressure	x		
Physical Activity			
CARDIA/EARLY Q – sedentary behavior	x		x
Diet			
Block Dietary Fat Q	x		x
Block Dietary Fruit/Vegetable Q	x		x
EARLY Eating Away from Home Q	x		x
EARLY SSB Consumption Q	x		x
NHIS Screener	x		x
Satisfaction			
Consumer Satisfaction & Helpfulness Q			x
Other Measures			
Palatable Eating Motives Scale (PEMS) – Coping Subscale	x		x
Reward-based Eating Drive (RED) Scale	x		x
Important Others Q	x		x
Medical Events			x
Perceived Stress Scale (PSS)	x		x
Ambulatory Screening for COVID-19	x		x

General Assessments

Demographics. We will collect demographic information such as age, sex, race, and ethnicity. We will also assess how often they attend the program.

We will use several measures and data sources to assist in determining eligibility for the study. **Exercise pre-participation screening (modified 2018 PAR-Q):** This modified physical activity readiness questionnaire will be used to assess if consumer is able to participate in exercise classes. **Medical History:** We will collect medical history information from each consumer to assess ability to participate in the ACHIEVE program and the staff. **Medications:** We will list all of the consumer's current medications. We will use the *Readiness Rulers* survey to assess participant's readiness to lose weight and willingness to participate in the ACHIEVE program.

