
Medical events. We will also capture any medical events that occur during the 6-month intervention.

Important others. We will capture information about support systems and people in the consumer's life that can assist in healthy weight management behaviors.

Intervention process measures. During the weight management curriculum, attendance, participation and weight measurements will be collected.

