15. POTENTIAL RISKS

Potential risks differ by study population.

All research studies have some degree of risk or discomfort. Time burden in responding to surveys and discomfort during interviews using sensitive questions are common risks and discomforts of minimal risk studies that use an oral consent process.

Staff participants may become tired or bored during surveys, interviews or focus groups.

There are risks related to physical activity and nutrient intake, including hypoglycemia and symptomatic hypotension related to diet and exercise interventions. Protections against these risks are described below. We have also set alert values for baseline blood pressure data collection, we have procedures in place for surveillance and reporting, and our exclusion criteria is meant to exclude people for safety reasons.

Consumers will be screened for orthopedic or rheumatologic problems that might limit their ability to participate in the physical activity component of the intervention. Exercise will focus on mild to moderate intensity aerobic exercise using progression of intensity and duration appropriate for sedentary individuals. If there is any question about the etiology of an injury or the need for treatment, the consumer will be referred to a physician for further evaluation.

Surveillance for serious adverse events and other relevant clinical events that may be associated with study participation will occur at the six month mark. This is done using a standardized questionnaire. In addition to the end of study report participants may report events in other settings (e.g., intervention contacts). A study clinician will review the completed forms, will classify the event according to several dimensions (expectedness, relatedness and type) and will take appropriate action. Safety-related events will be reported in a timely fashion as required by the IRB and NIMH.

Expected events

Over the duration of the six month project a number of medical events may be expected to occur in overweight or obese adults, including routine surgeries and procedures, the development of cancer and other chronic conditions, increased symptoms from a chronic condition, musculoskeletal problems and motor vehicle accidents.

Importance of knowledge to be gained

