Blood pressure: Alert level 1: For any systolic blood pressure (SBP) measure of ≥ 180 mmHg or diastolic blood pressure (DBP) of ≥ 110 , the participant is notified during the visit, the study clinician is contacted and the subject is referred to their personal physician for further evaluation within one week. Alert level 2: For any systolic blood pressure (SBP) measure of ≥ 160 mmHg or diastolic blood pressure (DBP) of ≥ 100 , the participant is notified during the visit, the study clinician is contacted within 1 week and the subject is referred to their personal physician for further evaluation within one month. Alert level 3: For any systolic blood pressure (SBP) measure of ≥ 140 mmHg or diastolic blood pressure (DBP) of ≥ 90 , the participant is notified during the visit, the study clinician is contacted per routine reporting and the subject is referred to their personal physician for further evaluation within two months. For any elevated blood pressure values, if the participant is symptomatic with chest pain, headache or shortness of breath, the study clinician and primary care physician are notified immediately. For any systolic blood pressure (SBP) measure of <90 mmHg or diastolic blood pressure (DBP) of <50 , the participant is notified during the visit, the study clinician is contacted per and the subject is referred to their personal physician for further evaluation within one week. If the participant has symptoms of lightheadedness or feeling faint, the study clinician and primary care physician are notified immediately.

Mental Health

If a participant is hospitalized for psychiatric reasons during the study, he/she will be reassessed by rehabilitation program staff and study personnel after return to the rehabilitation program for the ability to continue in the curriculum. We have enrolled over 800 people from a similar population in clinical trials, and we expect these occurrences to be rare.

Pregnancy and other exclusions

If a participant becomes pregnant during the study, she is then excluded. If a participant develops cancer, unstable angina, or another condition for which weight loss or exercise might be contraindicated, further participation will be determined by the participant's primary care physician in conjunction with a study clinician.

Surveillance and Reporting Procedures

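### Serious adverse events and medical events are actively sought only once, by a six-month questionnaire, so several in-study safety provisions depend on events being volunteered

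*Combined protocol and SAP*

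**What the plan says.** Section 14 (Safety Monitoring for Consumer Participants): "Surveillance for serious adverse events and other relevant clinical events will occur at the six-month mark". Section 15 repeats the timing and names the instrument: surveillance "will occur at the six month mark. This is done using a standardized questionnaire". Table 5 in Section 7.3 agrees: the row "Medical Events" is marked only in the 6M Post column, with nothing under During. The text of Section 7.3 nevertheless sets a wider target: "We will also capture any medical events that occur during the 6-month intervention".

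There is a second, passive route. Section 15 adds that "participants may report events in other settings (e.g., intervention contacts"). Section 14 names a study clinician, covered round the clock, as the person whom staff, participants and physicians contact on medical matters. On reporting, Section 15 says: "Safety-related events will be reported in a timely fashion as required by the IRB and NIMH".

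Section 3 lists "memory impairment, limited executive function, and residual psychiatric symptoms" among the difficulties particular to this population.

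**The concern.** A single end-of-study questionnaire has to recover six months of events by recall, from people whose memory the protocol itself describes as impaired. Sections 14 and 16 also contain provisions that can work only if an event is known close to when it happens. If the schedule is followed exactly as written, an event that nobody mentions stays unknown until month 6, when those provisions can no longer serve their purpose. An event forgotten by then may never be recorded.

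What is at stake is the completeness and timeliness of safety data on up to 120 consumers (Section 4), in a trial with one independent monitor and no data safety monitoring board (Section 16). The primary outcomes, which are measured on coaches, are not affected.

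**Working it through.** The plan gives no figure to reproduce. The check has two parts: a comparison of the provisions with their sources of information, and a short calculation of delay.

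**Step 1. What does each in-study provision rely on to learn of an event?**

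- *Marked weight loss (Section 16).* Weigh-ins take place on each class day (Exhibit 1, Section 11.1), so this has its own source for consumers who attend.
- *Psychiatric hospitalization (Section 16).* "If a participant is hospitalized for psychiatric reasons during the study, he/she will be reassessed by rehabilitation program staff and study personnel" once back at the program. Program staff see the person return, so this also has its own source.
- *Symptomatic hypotension (Section 16).* Staff are to inform the primary physician, but Table 5 schedules blood pressure at baseline only. During the study it can surface only through a report of symptoms, and participants are directed to their own physician.
- *Pregnancy, cancer, unstable angina (Section 16).* No scheduled measurement or question before month 6, so these depend on spontaneous reports.
- *Continuing after a new medical problem (Sections 14 and 16).* The same applies. The two sections also assign the lead in this judgement differently, one to the study clinician and the other to the primary care physician, and should be reconciled.
- *Serious adverse events (Section 16).* The subsection on surveillance and reporting procedures contains only a definition. It gives no duty on coaches or site staff, no route from site to clinician, and no time limit. The definition begins with death, which a participant questionnaire cannot record.

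**Step 2. Delay for an event that nobody volunteers.**

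Inputs: one look at T = 6 months (Sections 14 and 15; Table 5). Assumptions: event time t is uniform on 0 to 6 months, and the event is remembered when asked about.

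- Delay = T − t, so the range is 0 to 6 months.
- Mean = (1/6) × ∫₀⁶ (6 − t) dt = (1/6) × (36 − 18) = 3 months.
- An event in the first month (t between 0 and 1) is found 5 to 6 months later.
- With a prompt every month, mean delay = ∫₀¹ (1 − u) du = 0.5 month, and the maximum is 1 month.

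**Step 3. Allowing for the passive route.**

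Let p be the share of events volunteered, with no delay for those. The documents give no value for p. Averaged over all events, the mean delay is (1 − p) × 3 months under the plan and (1 − p) × 0.5 month with monthly prompting:

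| assumed p | plan (months) | monthly prompt (months) |
|---|---|---|
| 0 | 3 | 0.5 |
| 0.25 | 2.25 | 0.375 |
| 0.5 | 1.5 | 0.25 |
| 0.75 | 0.75 | 0.125 |

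The 3-month figure therefore describes unvolunteered events only. The table does not count events forgotten by month 6.

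**The case against.** The strongest reply is that the plan does not rely on the questionnaire alone. Events can be raised at intervention contacts, a clinician is always reachable, exercise sessions are supervised, primary care physicians are asked to monitor hypertension and diabetes, and medical exclusions are extensive. This is a six-month pilot that the protocol calls minimal risk, and a manual of operations that is not public may hold further procedures. All of this is fair and keeps the point modest. It does not close the gap: clinician cover helps only if the clinician is told, and the public text makes telling optional.

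Three stronger readings are tempting, and the documents do not support them.

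- *The single look breaches the commitment to timely reporting.* That commitment is tied to IRB and NIMH requirements that the documents do not reproduce, and the passive route exists. No breach can be shown.
- *Consumers who drop out are under no surveillance.* Nothing restricts the six-month questionnaire to attenders, and Section 7.2 allows collection by phone or Zoom for those who cannot come to the center. Some may be lost, but they are not excluded.
- *Event reporting will differ by arm.* The enhanced arm's extra monthly contact is with the coach, about curriculum delivery (Section 11.3). Both arms hold approximately monthly meetings with the study team (Section 11.2), and Section 13 does not describe a between-arm comparison of adverse events.

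It can also be said that more frequent asking costs more than it appears to. Five added rounds (months 1 to 5) for up to 120 consumers is up to 5 × 120 = 600 short prompts. Section 9 expects data collectors to be trained and certified, and a group weigh-in is not a private setting. These points stand and shape the fix.

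**Conclusion.** The point holds as a gap in event capture. Active collection is scheduled once, and the provisions on pregnancy, cancer, unstable angina, symptomatic hypotension and continuing after a medical problem have no stated source before month 6 other than volunteered reports. Marked weight loss and return after psychiatric hospitalization do have one.

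On size, unvolunteered events may be missed, or learned of on average 3 months late instead of about 0.5 month. This rests on uniform event timing and on recall when asked. Because the volunteered share is unknown, the average delay over all events cannot be estimated from the documents. The change is worth making because it is cheap and improves safety data.

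**What to change.** This concerns data capture only; no clinical rule is proposed.

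1. In Table 5, mark medical events under During as well as at 6M Post.
2. Prompt for events about monthly, at contacts that both arms already have: a brief question asked privately at a class weigh-in, and a standing item with site staff at the organizational strategy meeting, or in a private follow-up to it. The staff item should cover hospitalizations, deaths and other events, including those of consumers who no longer attend.
3. Send positive answers to the study clinician on the existing form.
4. Keep the six-month questionnaire for all enrolled consumers, by phone if needed.
5. Bring Section 7.3 (Table 5 and the medical events text) and Sections 14, 15 and 16 into line with this schedule, and state who passes events on and by what route.

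Cost: a few minutes of coach, site and study-team time each month, plus brief instruction of those who ask. No new visit or staff post is needed, and asking site staff about non-attenders avoids a new round of calls during the study.

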15. POTENTIAL RISKS

Potential risks differ by study population.

All research studies have some degree of risk or discomfort. Time burden in responding to surveys and discomfort during interviews using sensitive questions are common risks and discomforts of minimal risk studies that use an oral consent process.

Staff participants may become tired or bored during surveys, interviews or focus groups.

There are risks related to physical activity and nutrient intake, including hypoglycemia and symptomatic hypotension related to diet and exercise interventions. Protections against these risks are described below. We have also set alert values for baseline blood pressure data collection, we have procedures in place for surveillance and reporting, and our exclusion criteria is meant to exclude people for safety reasons.

Consumers will be screened for orthopedic or rheumatologic problems that might limit their ability to participate in the physical activity component of the intervention. Exercise will focus on mild to moderate intensity aerobic exercise using progression of intensity and duration appropriate for sedentary individuals. If there is any question about the etiology of an injury or the need for treatment, the consumer will be referred to a physician for further evaluation.

Surveillance for serious adverse events and other relevant clinical events that may be associated with study participation will occur at the six month mark. This is done using a standardized questionnaire. In addition to the end of study report participants may report events in other settings (e.g., intervention contacts). A study clinician will review the completed forms, will classify the event according to several dimensions (expectedness, relatedness and type) and will take appropriate action. Safety-related events will be reported in a timely fashion as required by the IRB and NIMH.

Expected events

Over the duration of the six month project a number of medical events may be expected to occur in overweight or obese adults, including routine surgeries and procedures, the development of cancer and other chronic conditions, increased symptoms from a chronic condition, musculoskeletal problems and motor vehicle accidents.

Importance of knowledge to be gained

Persons with SMI have high burdens of each major cardiovascular risk behavior, yet persons with SMI have been systematically excluded from interventions to decrease cardiovascular risk. If successful, this proposed program and curriculum could be disseminated widely. The minimal health risks to participants are offset by the potential benefits to participants and to the greater population with chronic mental illness.

16. ADEQUACY OF PROTECTION AGAINST RISKS

Organization staff will be appropriately recruited and informed of the study by study team with waiver of documentation of informed consent. They study team will inform them that they do not have to answer any questions they do not want to, and that their employment or evaluations will not be affected by their responses. This is a minimal risk study.

There will not be a Data Safety Monitoring Board (DSMB) for this project. Participant safety will be closely monitored. We will have an independent study monitor who is experienced in clinical trial lifestyle interventions [name], a practicing internist, who will work with Drs. [name] to promote and monitor safety throughout the study. The safety officer does not provide direct medical care and is not involved in the intervention.

Protection of research participants begins with the eligibility criteria, which are designed to exclude individuals with a serious medical condition that would preclude their ability to lose weight or to exercise safely. This will be done in collaboration with the participant's primary care physician. During the study, clinical care will be provided by the participants' usual specialty mental health providers and the primary care physician, not by the study. Participants will be made aware of this delineation of responsibility. We will carefully monitor the safety of enrolled participants. If a participant develops a medical problem, the safety of continuing or resuming the intervention will be ascertained by the participant's primary care physician in collaboration with a study clinician.

Physical activity: The small risk during physical activity will be minimized by emphasizing moderate activity, and by following American College of Sports Medicine guidelines regarding need for medical examination prior to beginning an exercise program. Trained exercise interventionists will supervise all exercise sessions.

Nutrient intake: Calorie restriction could theoretically lead to inadequate nutrition or excessive, rapid weight loss. Intervention subjects will be encouraged to eat a variety of foods from all food groups and maintain an adequate caloric level. Those who have a sudden, marked weight reduction will be interviewed to determine if extreme measures have been taken. The issue of adequate nutrient intake and the importance of safe weight loss will be discussed in the group and individual sessions. If a problem is suspected, the participant will be counseled.

Hypoglycemia related to diet and exercise interventions: For patients who may be susceptible to hypoglycemia due to use of anti-diabetic medications, weight loss interventions have the potential to increase the risk of hypoglycemia, especially during the time when diet and/or physical activity interventions are implemented. To minimize the risk of hypoglycemia, we will require primary care physician approval prior to enrolling individuals with diabetes.

Symptomatic hypotension related to diet and exercise interventions: For patients who may be susceptible to hypotension because they are using medications that lower blood pressure, weight loss interventions have the potential to increase the risk of hypotension. Participants are educated about symptoms of hypotension and urged to contact their primary physician if they have symptoms suggestive of hypotension. In addition, staff will notify primary physicians for participants who develop symptomatic hypotension while on anti-hypertensive medications.

Alert Values for baseline blood pressure data collection

Blood pressure: Alert level 1: For any systolic blood pressure (SBP) measure of ≥ 180 mmHg or diastolic blood pressure (DBP) of ≥ 110 , the participant is notified during the visit, the study clinician is contacted and the subject is referred to their personal physician for further evaluation within one week. Alert level 2: For any systolic blood pressure (SBP) measure of ≥ 160 mmHg or diastolic blood pressure (DBP) of ≥ 100 , the participant is notified during the visit, the study clinician is contacted within 1 week and the subject is referred to their personal physician for further evaluation within one month. Alert level 3: For any systolic blood pressure (SBP) measure of ≥ 140 mmHg or diastolic blood pressure (DBP) of ≥ 90 , the participant is notified during the visit, the study clinician is contacted per routine reporting and the subject is referred to their personal physician for further evaluation within two months. For any elevated blood pressure values, if the participant is symptomatic with chest pain, headache or shortness of breath, the study clinician and primary care physician are notified immediately. For any systolic blood pressure (SBP) measure of <90 mmHg or diastolic blood pressure (DBP) of <50 , the participant is notified during the visit, the study clinician is contacted per and the subject is referred to their personal physician for further evaluation within one week. If the participant has symptoms of lightheadedness or feeling faint, the study clinician and primary care physician are notified immediately.

Mental Health

If a participant is hospitalized for psychiatric reasons during the study, he/she will be reassessed by rehabilitation program staff and study personnel after return to the rehabilitation program for the ability to continue in the curriculum. We have enrolled over 800 people from a similar population in clinical trials, and we expect these occurrences to be rare.

Pregnancy and other exclusions

If a participant becomes pregnant during the study, she is then excluded. If a participant develops cancer, unstable angina, or another condition for which weight loss or exercise might be contraindicated, further participation will be determined by the participant's primary care physician in conjunction with a study clinician.

Surveillance and Reporting Procedures

Serious adverse events include the following: death, life-threatening experience, inpatient medical or surgical hospitalization, persistent or significant disability or incapacity. Important medical events that do not result in death or require hospitalization may be considered serious adverse events if they jeopardize the participant or require medical or surgical intervention to prevent one of the outcomes above.

Breach of confidentiality

All participant information will be considered confidential. This confidentiality will be assured through several mechanisms. For the study, each participant will be assigned an anonymous study ID, which will be used on all study forms. In addition, all study forms and paper records that contain participant information will be kept in secured, locked areas when not in use. During active data collection, any hard copies of data collection forms will be stored in locked areas. Only authorized personnel will have access to these locked areas. Finally, neither the rehabilitation program nor participants will be identified by name in any publications.

For qualitative data, no focus group participants will be individually identified; a site identifier will be used. The link to the site ID will be held in a locked file. Focus group transcripts will have names (if mentioned during the group) removed, and no participants will be identified by name in any publications. The tapes will be kept for 7 years and then destroyed. Furthermore, data will not be presented in such a way that identity can be inferred. Transcripts of focus groups will have names removed. Employees will be assured that their participation in the study and information shared in the interviews will not affect their employment or their evaluation. As described in Data Management and Security, data will be stored in Johns Hopkins secure drives.

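### The serious adverse event definition does not make a psychiatric admission serious as such, so a serious event summary built on it would be incomplete for consumers with serious mental illness

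*Combined protocol and SAP*

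**What the plan says.** The definition is in Section 16, under Surveillance and Reporting Procedures: "Serious adverse events include the following: death, life-threatening experience, inpatient medical or surgical hospitalization, persistent or significant disability or incapacity". The next sentence allows some further events to be upgraded: "Important medical events that do not result in death or require hospitalization may be considered serious adverse events if they jeopardize the participant", or if they need medical or surgical treatment to prevent one of the listed outcomes.

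Psychiatric admissions are dealt with separately, in the Mental Health paragraph of Section 16: "If a participant is hospitalized for psychiatric reasons during the study, he/she will be reassessed by rehabilitation program staff and study personnel". That reassessment takes place after the consumer returns to the program and concerns the ability to continue. The paragraph adds that "we expect these occurrences to be rare". It gives no seriousness classification and no reporting step.

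Two other sections bear on the point:

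- Section 14 (Safety Monitoring for Consumer Participants) says of the study clinician, who is also identified as the independent study monitor: "This clinician will review and report any serious adverse events". On timing and scope it says: "Surveillance for serious adverse events and other relevant clinical events will occur at the six-month mark".
- Section 15 adds a standardized questionnaire, allows events to be reported in other settings, has a study clinician classify each event by type, relatedness and expectedness, and commits to reporting safety-related events as the IRB and NIMH require.

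**The concern.** Under the Section 16 wording, any inpatient medical or surgical stay is serious whatever its cause. That includes a planned operation, although Section 15 lists routine surgery among the events to be expected. An inpatient psychiatric stay is not serious on the same ground. Yet every consumer in the trial has serious mental illness (Section 7.1), and Section 16 itself foresees psychiatric admission and treats it as reason enough to review participation.

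What is at stake is the completeness of the serious event count. The study clinician reviews and reports serious adverse events, so the definition fixes what enters that stream under that label. There is no data safety monitoring board (Section 16), and oversight rests on the independent monitor. A reader who sees a low serious event count could take it as reassurance about a kind of event that the definition did not ask anyone to count.

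**Working it through.** No arithmetic settles this, and the plan gives no figure to reproduce. The check is whether any route in the text makes a psychiatric admission serious.

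1. **The hospitalization criterion.** It is qualified by two adjectives, medical and surgical. Could the first cover psychiatric stays? The protocol's own usage is against that. Section 14 writes "If a participant develops a medical or psychiatric issue", which treats the two as alternatives, and the same section pairs a serious medical condition with psychiatric instability as separate grounds for exclusion.

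2. **The upgrade sentence.** It applies to events that did not require hospitalization. An admission falls outside it by its own terms, so it cannot bring psychiatric admissions back in.

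3. **The other listed criteria.** Death, a life-threatening experience and lasting or significant disability apply whatever the cause. A psychiatric admission that meets one of them is serious on that ground. One that meets none of them is not.

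4. **The Mental Health paragraph in Section 16.** It leads to a decision about continuing in the curriculum. It neither assigns seriousness nor directs a report.

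5. **The classification step in Section 15.** Seriousness is not among the dimensions listed, so no stated step would reclassify a psychiatric admission.

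6. **General capture and reporting in Sections 14 and 15.** Surveillance extends beyond serious events to other relevant ones, and safety-related events go forward as the IRB and NIMH require. A psychiatric admission may be recorded or reported this way, but neither provision makes it serious.

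**Size.** A count of affected events would be the number of consumers multiplied by a six-month admission rate. Section 4 gives the first factor as at most 120. The documents give no value for the second, only the expectation of rarity, so the product cannot be formed. What can be shown is the weight of one case: with 120 consumers enrolled, one whose only serious event was a psychiatric admission changes the proportion with a serious event by 1/120 = 0.83 percentage points. That shows sensitivity to a single case; it is not an estimate of how many there will be.

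**The case against.** A reader might infer that psychiatric admissions will go unreported as serious, or will be unseen by the IRB, the funder and the monitor. The documents do not support that, for four reasons:

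- The definition says that serious events include those listed. This is not strictly a closed list, and no sentence expressly excludes psychiatric admissions.
- The reporting clause in Section 15 is wider than serious events. What the IRB and NIMH require is not reproduced, so non-reporting cannot be shown.
- Section 14 has the study clinician judge whether it is safe to continue when a psychiatric issue arises, and identifies that clinician as the independent monitor. The monitor may therefore know of the admission whatever label it carries.
- The questionnaire, the medical events form listed in Table 5 and the manual of operations mentioned in Section 9 are not reproduced. They may already record psychiatric admissions.

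It can also be said that the separate Mental Health paragraph may be deliberate in a study described as minimal risk, and that the Section 14 sentence on psychiatric issues concerns continued participation, not seriousness.

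All of this stands as a limit on the consequences. It does not supply the missing classification. A list that is not strictly closed leaves the matter to individual judgment, and wider capture does not put an event into the serious count. If the omission is deliberate, the protocol gives neither the reason nor another way of tabulating these admissions.

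**Conclusion.** The point holds as one of classification. Under the stated definition a psychiatric admission is not, as such, serious; it becomes so only by meeting another criterion. A serious event summary built on that definition would be incomplete for a population in which such admissions are foreseeable and are foreseen by the protocol.

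It is not established that these admissions go unrecorded or unreported, or that the monitor would not learn of them. The number affected cannot be estimated from the documents.

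The effect is confined to safety reporting. The primary outcomes are the coaches' knowledge, self-efficacy and fidelity (Section 4), and none depends on this wording. The conclusion rests on two readings: that medical does not include psychiatric, as the protocol's own usage indicates, and that a serious event summary will follow the Section 16 definition. Section 13 specifies no safety tabulation that would say otherwise.

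**What to change.** Reconcile the Mental Health paragraph with the definition in Section 16. Word the hospitalization criterion as *inpatient hospitalization (medical, surgical or psychiatric)*, and state that psychiatric admissions are classified and counted with the other serious events. Check that the six-month questionnaire and the medical events form ask about them, and amend these only if they do not.

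The change affects reporting only. The rules in Section 16 on reassessment and continued participation stay as they are. The cost is a few words in the protocol and a few more event reports for the study clinician to review.
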